## 5.2.3. Analyses for Time-to Event Endpoints

Time-to event endpoint will also be summarized using the Kaplan-Meier method (product-limit estimates) and estimated survival curves will be displayed graphically when appropriate. Graphs will describe the number of participants at risk over time. The median, quartiles, and probabilities of an event at particular points in time will be estimated by the Kaplan-Meier method. Confidence intervals for medians and quartiles are based on the Brookmeyer-Crowley method. Confidence intervals for the estimated probability of an event at a particular time point will be generated using the Greenwood formula.

A stratified log-rank test with stratification factors will be performed to test for differences between the voxelotor and placebo treatment groups.

A stratified Cox regression model with treatment group as the covariate will be used to estimate the treatment group hazard ratio (voxelotor vs. placebo) and the corresponding two-sided 95% confidence interval.

Counts and percentages of subjects who experienced the event as well as the counts and percentages of subjects who were censored and the type of censoring (eg, death or missing data) will be reported for each of the treatment groups.

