## 8.1. Analysis Populations

Two main analysis populations are defined for this study: the intent-to-treat (ITT) population and the safety-evaluable population.

The ITT population includes all randomized participants. For analyses based on this population, participants will be grouped according to the treatment assigned at randomization. This is the primary analysis population for efficacy, demographics, and baseline characteristics data.

The safety-evaluable population includes all participants who receive at least 1 dose of study drug. For analyses based on this population, participants will be grouped according to the actual study treatment received. This is the primary analysis population for safety and exposure data.

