## 8.4.2. Secondary Endpoints

Time to resolution of target ulcer(s) up to Week 12: a stratified log-rank test will be used to compare the treatment groups. A Cox regression model will be used to estimate the hazard ratio between voxelotor +SOC and placebo + SOC groups, as appropriate. Time to resolution will be measured (in days) from Day 1 to date of initial closure of the target ulcer. For participants with more than one target ulcer, time to resolution will be based on the time to closure of all target ulcers (ie, initial closure of the last target ulcer to resolve).

Change from baseline in sum of surface area of target ulcer(s) at Week 12: a mixed-effect model for repeated measures will be used to estimate and compare change from baseline in sum of target ulcer(s) surface area between voxelotor + SOC and placebo + SOC groups. The model will include terms for treatment group, study visit, treatment-by-study visit interaction, as well as the stratification factors. Within-participant variability will be modeled using an unstructured covariance matrix.

Incidence of new ulcers by Week 12: the proportion of participants with new ulcer occurrence within 12 weeks of treatment will be compared between treatment groups using a CMH test, stratified by target ulcer size, and target ulcer duration, as appropriate.

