#### 2. INTRODUCTION

This SAP provides the detailed methodology for summary and statistical analyses of the data collected in Study GBT440-042 for the final CSR after last subject last visit (LSLV). This document may modify the plans outlined in the protocol, however, any major modifications of the primary endpoint definition or its analysis will also be reflected in a protocol amendment. Statistical analyses will be performed using cleaned case report form (CRF) data as well as non-CRF data (i.e., blood samples data and banked biospecimens).

The administration of the study intervention was voluntarily paused by the Sponsor on 10 May 2024 due to the overall number of deaths observed in the study. The decision was made by the sponsor to terminate the study on 25 September 2024 and the LSLV was on 22 October 2024.

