## 3.2. Secondary Endpoint(s)

Time (in days) to resolution of target ulcer(s) up to Week 12

Time to resolution of target ulcer(s) is defined as

Date of resolution – Date of randomization +1,

where the date of resolution is defined as the first time of the observed ulcer was resolved. For participants with more than one target ulcer, time to resolution of target

> PFIZER CONFIDENTIAL TMF Doc ID: 98.03 Page 16 of 43

[figure not shown]
ulcer(s) is defined as time to the last target ulcer confirmed resolved. For participants who do not have the last target ulcer confirmed resolved by Week 12 or who are discontinued from study, the time to resolution will be censored.

- Change from baseline in total surface area of target ulcer(s) at Week 12
- Incidence of new ulcers by Week 12

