## 5.3.1. Status of Target Study Ulcer(s)

Participants who are lost to follow-up or otherwise drop out of the study without confirmation of resolution of all target study ulcer(s) prior to Week 12, will be classified as non-responders for purposes of the primary analysis.

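### Kaplan-Meier with death as censoring can overstate the probability of ulcer resolution; the curves, medians and Week 12 probabilities should treat death as a competing event

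*SAP*

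**What the plan says.** SAP 5.2.3 sets the method for time-to-event endpoints: "The median, quartiles, and probabilities of an event at particular points in time will be estimated by the Kaplan-Meier method". It also plans counts and percentages, by arm, of participants with the event and of those censored, broken down by "the type of censoring (eg, death or missing data". Death therefore stands beside missing data as a reason for censoring. SAP 3.2 adds that for participants without confirmed resolution by Week 12, or "who are discontinued from study, the time to resolution will be censored". Neither section gives the date at which such a participant is censored.

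The protocol (8.4.2) names only the test and the hazard-ratio model: "Time to resolution of target ulcer(s) up to Week 12: a stratified log-rank test will be used", with Cox regression for the hazard ratio. Appendix 1 of the SAP places the Kaplan-Meier curves in the main-analysis column for this endpoint. Neither document mentions cumulative incidence, competing risks or a sensitivity analysis for death.

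The primary analysis works differently. Under SAP 5.3.1, participants "lost to follow-up or otherwise drop out of the study without confirmation of resolution of all target study ulcer(s" before Week 12 "will be classified as non-responders for purposes of the primary analysis". The denominator is everyone randomized (protocol 8.1: "The ITT population includes all randomized participants"). Death is not named in that rule.

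SAP section 2 records that the sponsor paused dosing on 10 May 2024 "due to the overall number of deaths observed in the study".

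**The concern.** A participant who dies with an open ulcer can no longer heal. Kaplan-Meier censoring at death passes that participant's weight to the survivors still at risk, so the curve describes healing as if nobody could die. That is a hypothetical quantity. The probability a reader expects at Week 12 is the share of randomized participants who healed.

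Three outputs are exposed: the Week 12 probability, the median and quartiles, and the visual contrast between arms if deaths are unequal. The same participant would in all likelihood be a failure in the primary proportion, so one report could show two Week 12 resolution rates for the same arm, partly for this reason. Deaths did occur in this study, and SAP version 4 was written after the pause, so the handling of death needs a deliberate choice.

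**Working it through.** **Inputs.** The documents give no figure for the healing curves, so there is none to reproduce. From the documents: 40 per arm (SAP 2.3.1), visits every 2 weeks to Week 12, hence six post-baseline visits (protocol Appendix 1), and 5% assumed dropout by Week 12 (protocol 8.6). Assumed, because no document gives them: the resolved share F_R and the share dying unhealed F_D, by Week 12. With 40 per arm, F_D of 2.5%, 5% and 10% means 1, 2 and 4 deaths.

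**Step 1: size of the excess.** With constant cause-specific hazards per visit:
- total hazard q = 1 − (1 − F_R − F_D)^(1/6)
- resolution hazard h = q × F_R / (F_R + F_D)
- Kaplan-Meier with death censored gives 1 − (1 − h)^6; the cumulative incidence is F_R.

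Example with F_R = 0.55 and F_D = 0.05: q = 1 − 0.40^(1/6) = 0.1416; h = 0.1416 × 0.55/0.60 = 0.1298; 1 − 0.8702^6 = 0.566. The excess is 1.6 points.

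| Resolved | 2.5% deaths | 5% deaths | 10% deaths |
|---|---|---|---|
| 20% | 0.23 | 0.47 | 0.98 |
| 55% | 0.77 | 1.58 | 3.35 |
| 70% | 1.11 | 2.29 | 4.92 |

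Entries are excess percentage points. If deaths in each interval fall just before the visit, the resolution hazard becomes h/(1 − d), where d = q × F_D/(F_R + F_D). The excess is then somewhat larger: 4.3 points at 55% and 6.1 at 70%, both with 10% deaths.

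**Step 2: the median.** Take 40 participants with resolutions at the six visits of 3, 3, 4, 3, 3, 3 (19 in all, 47.5%) and one death just before each of visits 1, 3, 4 and 6. Then S = 36/39 × 33/36 × 28/32 × 24/27 × 21/24 × 17/20 = 0.489. Kaplan-Meier reports 51.1% resolved and a median at Week 12, although fewer than half healed.

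**Step 3: the contrast.** Let both arms resolve 20 of 40, as 4, 3, 3, 3, 3, 4.
- Six deaths, one before each visit: S = 35/39 × 31/34 × 27/30 × 23/26 × 19/22 × 14/18 = 0.438, so 56.2%.
- One death, before visit 3: S = 36/40 × 33/36 × 29/32 × 26/29 × 23/26 × 19/23 = 0.490, so 51.0%.

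The curves differ by 5.2 points where the resolved proportions are equal. Six deaths in one arm is an illustration only.

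**Step 4: what remains after the change.** Add 5% living dropouts, censored here but non-responders in the primary analysis. With F_R = 0.55, 5% deaths and 5% dropout, q = 1 − 0.35^(1/6) = 0.1605, h = 0.1358 and the death hazard d = 0.01235.
- Kaplan-Meier: 1 − (1 − h)^6 = 0.583, about 3.35 points above 55%.
- Aalen-Johansen: h/(h + d) × [1 − (1 − h − d)^6] = 0.9167 × 0.618 = 0.566, about 1.6 points above 55%.

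With 5% dropout and no deaths, Kaplan-Meier already gives 56.6%. Treating death as a competing event removes the death part of the gap and leaves the dropout part.

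**The case against.** The strongest reply is that nothing inferential changes. The log-rank test and Cox model are the only analyses the protocol names for this endpoint, and both are valid cause-specific comparisons with death censored. SAP 5.2.3 offers Kaplan-Meier as an additional summary and already plans, by arm, the percentage with the event and the censoring by type. A reader can see resolved over randomized, and the deaths, next to the curve. This stands: the gap is partly visible and no test is affected.

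The size argument also has force. At 55% resolved with 40 per arm, the 95% half-width is 1.96 × √(0.55 × 0.45/40) = 15 points, against an excess of about 1 to 2 points for one or two deaths. But sampling error does not justify a known upward bias that is easy to remove.

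The text is also open. No censoring date is given; if unhealed deaths were carried to Week 12, the bias would vanish. Listing death as a censoring type makes censoring at death the likelier reading, but it is not written.

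A reader might infer more than the documents support:
- That the reason given for the pause shows material bias. It covers the whole study, open-label treatment included, and gives no number, arm or timing. Only unhealed deaths before Week 12, followed by a later resolution in the same arm, matter.
- That the SAP contradicts itself. A non-responder proportion and a time-to-event curve answer different questions, and death as failure is inferred from the general dropout wording.
- That a competing-risk curve would match the primary proportion. It would not while living dropouts are censored.

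**Conclusion.** The point holds for the descriptive time-to-event output: curves, quartiles, median and Week 12 probabilities. If death is censored when it occurs, these overstate resolution under the condition given above. The excess is under 2.5 points for up to 5% deaths in every scenario tabulated, and reaches about 3.4 points (55% resolved) or 4.9 points (70% resolved) only with 10% deaths. The resolution and death rates and the constant hazards are assumptions, and the true size cannot be computed from the documents. The primary test, the stratified log-rank test and the hazard ratio, read as cause-specific, stand as planned. This is a low-severity correction to reporting.

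**What to change.** Keep the stratified log-rank test and Cox model as written, and make four changes:

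1. In SAP 5.2.3 and Appendix 1, report the curves, quantiles and Week 12 probabilities as Aalen-Johansen cumulative incidence with death as a competing event. Keeping unhealed deaths at risk as unresolved to Week 12 gives the same result when death is the only loss; use that device for the curves only, so that the test and the hazard ratio stay cause-specific.
2. Keep the pre-specified Kaplan-Meier output as supplementary. SAP version 4 (16 December 2024) postdates last subject last visit (22 October 2024), so the change should be visible and dated.
3. In SAP 3.2, state the censoring date for each reason.
4. In SAP 5.3.1, name death in the non-responder rule, and add a note that living dropouts are censored in the curves but are non-responders in the primary analysis, so a small difference is expected.

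The cost is a few sentences and a standard software option; no new data are needed. The drawbacks are slightly lower reported healing probabilities and a late change to a descriptive display.

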#### 5.2.4. Correlation Analysis Between Continuous and Binary Endpoints

dichotomous variable will be used CCI

Pearson correlation with one
PFIZER CONFIDENTIAL

## 5.3. Methods to Manage Missing Data

Guidelines regarding how missing data will be handled are described below.

## 5.3.1. Status of Target Study Ulcer(s)

Participants who are lost to follow-up or otherwise drop out of the study without confirmation of resolution of all target study ulcer(s) prior to Week 12, will be classified as non-responders for purposes of the primary analysis.

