#### 8.4.1. Primary Endpoint

The primary endpoint will be measured by the proportion of participants achieving resolution of the target ulcer(s) during the 12-week Randomized Treatment Period.

The proportion of participants with resolution of target leg ulcer(s) by Week 12 will be analyzed using a Cochran-Mantel-Haenszel (CMH) test to compare voxelotor + SOC with placebo + SOC groups, stratified by target ulcer size and target ulcer duration.

. For participants with more than one target leg ulcer, all ulcers must be confirmed resolved in order for the participant to be considered a responder.

Participants who are lost to follow-up or otherwise drop out of the study without confirmation of resolution of all target study ulcer(s) prior to study dropout will be classified as non-responders for purposes of the primary analysis.

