### 8.7. Missing Data Handling

Participants who are lost to follow-up or otherwise drop out of the study without confirmation of resolution of all target study ulcer(s) prior to study dropout, will be classified as non-responders for purposes of the primary analysis.

Detailed considerations of missing data handling will be described in the SAP.

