## 2.3.2. Treatment Group and Reporting Period for Analysis

In the study schematic in Figure 1. Study Schema, the study period and treatment groups to be included in the primary and open-label analysis.

Efficacy and Safety: Primary analysis (Randomized Treatment Period):

- Treatment groups:
  - Voxelotor: participants randomized to voxelotor.
  - Placebo: participants randomized to placebo.
- Reporting Period:
  - From Day 1 through Week 12 for subjects who either do not achieve confirmed reepithelialization or achieve it before or at Week 12 visit.
  - From Day 1 through Week 14 for subjects who have the initial skin reepithelialization confirmed at Week 12 and then the 14-week visit will be used to confirm resolution.

Day 1 is defined as the date of randomization. The last day (i.e. Week 12 visit or Week 14) of randomized treatment period is defined as the last day entered on the disposition page for end of randomized treatment period.

Efficacy: Open-label analysis (Open-Label Treatment Period):

- Treatment groups:
  - Voxelotor: participants randomized to voxelotor who received at least one dose of voxelotor.

- Delayed voxelotor: participants randomized to placebo during Randomized Treatment Period (through Week 12) and who received at least one dose of voxelotor on or after the Week 12 visit.
- Total: participants who received at least one dose of voxelotor.

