# APPENDICES

# Appendix 1. Summary of Efficacy Analyses

Endpoint	Analysis Type	Population	Data Inclusion and Rules for Handling Intercurrent Events and Missing Data	Main Analysis Model
Primary				
The status of participants achieving resolution of the target ulcer(s) by Week 12	Exact CMH test Descriptive summary statistics Subgroup analysis	ITT	Participants who are lost to follow-up or otherwise drop out of the study without confirmation of resolution of all target study ulcer(s) prior to Week 12, will be classified as non- responder.	Exact CMH test with stratification factors of target ulcer size and duration
Secondary				
Time (in days) to resolution of target ulcer(s) up to Week 12	Log-rank and Cox regression model  Descriptive summary statistics  Subgroup analysis	ITT	For participants who do not have the last target ulcer confirmed resolved by Week 12 or who are discontinued from study, the time to resolution will be censored	Kaplan-Meier method (product-limit estimates) and estimated survival curves will be displayed graphically when appropriate. Graphs will describe the number of participants at risk over time. A stratified log-rank test with stratification factors will be performed to test for differences between the voxelotor and placebo treatment groups
Change from baseline in total surface area of target ulcer(s) at Week 12	LS means (95%CI) LS means difference Descriptive summary statistics Subgroup analysis	ITT	NA	MMRM analysis will be used as described in Section 5.2.2.1 with the stratification factors including target ulcer size (categorical) and target ulcer duration (categorical) as covariates and. The p-value for LS means difference (voxelotor vs. placebo) at Week 12 will be provided.

Endpoint	Analysis Type	Population	Data Inclusion and Rules for Handling Intercurrent Events and Missing Data	Main Analysis Model
Incidence of new ulcers by Week 12	Exact CMH test Descriptive summary statistics Subgroup analysis (age group and country)	ITT	NA	Exact CMH test with stratification factors of target ulcer size and duration
Exploratory				
The proportion of participants achieving resolution of the target ulcer(s) by Week 24	Descriptive summary statistics	ITT	NA	Descriptive statistics
Time (in days) to resolution of target ulcer(s) up to Week 24	Descriptive summary statistics	ITT	NA	Descriptive statistics

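### SAP 5.3.1 and Appendix 1 put an undeclared Week 12 cut-off into the primary non-responder rule; read in parallel with the protocol sentence, it fails participants confirmed at Week 12 or 14 who later leave

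*SAP*

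**What the plan says.** **Protocol.** Section 8.7 fails participants who "drop out of the study without confirmation of resolution of all target study ulcer(s) prior to study dropout, will be classified as non-responders". Section 8.4.1 and the synopsis state the same rule. The deadline is personal: what counts is whether resolution was confirmed before that participant left.

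**SAP.** Section 5.3.1 covers participants who "drop out of the study without confirmation of resolution of all target study ulcer(s) prior to Week 12, will be classified as non-responders". Appendix 1 repeats the new deadline in the primary-endpoint row: "without confirmation of resolution of all target study ulcer(s) prior to Week 12". SAP 2.1, which should list departures from the protocol's analysis plan, answers that there are none, and the visible version-history entries record no change to 5.3.1.

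**Confirmation after Week 12.** Footnote u of the protocol's Schedule of Assessments keeps participants whose ulcer first re-epithelializes at Week 12 on their assigned treatment for 2 more weeks to confirm resolution. SAP 2.3.2 extends the primary reporting period to match: "From Day 1 through Week 14 for subjects who have the initial skin reepithelialization confirmed at Week 12", with the Week 14 visit then serving as the confirmation.

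**The concern.** The rule decides who is a responder in the primary analysis, and the SAP's deadline does not fit the trial's own confirmation schedule. A closure first seen at Week 12 is confirmed at Week 14, so its confirmation can never precede Week 12. A confirmation made at the Week 12 visit does not precede Week 12 either.

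The phrase can be attached to two places in the sentence. Attached to the confirmation, as the corresponding phrase is in the protocol, it fails some participants whom the protocol would count as responders. Attached to the act of dropping out, it no longer names some participants whom the protocol names. Two programmers could code it differently, and the SAP does not say which is meant.

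Departures after Week 12 are plausible. SAP section 2 records that the sponsor paused dosing on 10 May 2024 and decided on 25 September 2024 to terminate the study. The documents give no counts of leavers and do not say whether leaving because of the termination counts as dropping out.

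**Working it through.** **1. The three rules applied to the same histories.** Reading A attaches the Week 12 phrase to confirmation; reading B attaches it to dropping out. Confirmation is taken to come one 2-week visit after first closure. This is inferred from the Week 12 to Week 14 arrangement, because the full definition is withheld. NR means non-responder.

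| History | Protocol 8.4.1/8.7 | SAP, reading A | SAP, reading B (rule alone) |
|---|---|---|---|
| Confirmed Week 6, leaves Week 8 | not failed | not failed | not failed |
| Closed Week 4, unconfirmed, leaves Week 5 | NR | NR | NR |
| Confirmed Week 10, leaves Week 16 | not failed | not failed | not addressed |
| First closed Week 10, confirmed Week 12, leaves Week 16 | not failed | **NR** | not addressed |
| First closed Week 12, confirmed Week 14, leaves Week 16 | not failed | **NR** | not addressed |
| First closed Week 12, unconfirmed, leaves Week 13 | NR | NR | **not addressed** |
| Never closed, leaves Week 13 | NR | NR | **not addressed** |

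Reading A departs from the protocol in rows 4 and 5 only. Reading B leaves the last two rows to the endpoint definition. SAP 3.1 requires all target ulcers to be confirmed resolved (that visible sentence concerns participants with more than one), and SAP 3.3 equates healing with confirmed re-epithelialization without that limit. On that definition the last two rows are non-responders and rows 3 to 5 remain responders, as in the protocol.

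**2. The plan's own power figure, for context.** Protocol 8.6 gives about 90% power for a 35-point difference with 40 per arm, two-sided 5%, Normal approximation. The control rate is not visible, so it is assumed over a range. With p̄ the mean of the two rates and n per arm:

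power = Φ{ [Δ − 1.96·√(2p̄(1−p̄)/n)] / √([p₁(1−p₁)+p₂(1−p₂)]/n) }

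For 20% versus 55% and n = 40: (0.35 − 1.96 × 0.1083)/0.1009 = 1.366, so power is 91.4%. Control rates of 10%, 15%, 25% and 30% give 95.4%, 93.2%, 90.1% and 89.5%. With 5% dropout removed (40 × 0.95 = 38 per arm), 20% versus 55% gives 89.9%. The stated figure is consistent with several control rates, so it cannot be tied to one.

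**3. Size per participant under reading A.** One reclassified participant moves an arm's rate by 1/40 = 2.5 points. At an assumed 15% versus 50%, rescoring 1, 2 or 3 voxelotor responders cuts the difference from 35 to 32.5, 30 or 27.5 points, and power from 93.2% to 89.5%, 84.7% or 78.7%. Rescoring a placebo responder would instead widen the difference, so the direction depends on who leaves.

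**4. How many responders could be exposed (illustration).** Assume a constant closure hazard and 2-weekly visits. The share of Week 12 responders first closed at Week 10 or 12 is [(1−p)^(8/12) − (1−p)]/p.

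- p = 55%: (0.587 − 0.450)/0.55 = 25%
- p = 20%: (0.862 − 0.800)/0.20 = 31%

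If 10%, 25% or 50% of these later leave, each arm's rate becomes p × (1 − late share × leaving share). The scored difference is then 34.2, 33.1 or 31.2 points, and power falls from 91.4% to 90.4%, 88.9% or 86.1%. At 30% versus 65%, power falls from 89.5% to 88.5%, 87.0% or 84.3%.

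**The case against.** The strongest reply is that reading A contradicts the SAP itself. SAP 2.3.2 uses the Week 14 visit to confirm closures first seen at Week 12, and recognises confirmation at the Week 12 visit. Section 5.3.1 sits under missing-data methods, and someone with confirmed resolution has no missing primary outcome. The primary analysis concerns the 12-week period, so leaving at Week 16 lies outside it. Reading B combined with the confirmed-resolution requirement returns the protocol's classification. Protocol 8.7 also leaves missing-data detail to the SAP.

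Much of this bears on what the authors probably meant, and it is a fair argument that reading A was not intended. It does not repair the sentence. Reading A is the one that runs parallel to the protocol sentence being replaced, and it is stated twice. Protocol 8.7 fixes this particular rule before delegating further detail, so substituting another deadline is more than elaboration.

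Three stronger inferences are tempting, and the documents do not support them:

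- **Both consequences at once.** Rescoring needs reading A; the unnamed Week 12 to 14 leavers need reading B. No single reading gives both.
- **Every confirmed responder who leaves later is at risk.** Those confirmed before Week 12 keep their status under reading A, and reading B rescores nobody.
- **Week 12 to 14 leavers have no classification.** The confirmed-resolution requirement makes an unconfirmed leaver a non-responder. The one reservation is that part of the primary definition is withheld.

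**Conclusion.** The SAP rule is wrong as written. It replaces the protocol's deadline in two places without declaring it. On the reading parallel to the protocol, it scores as failures participants whose resolution was confirmed at Week 12 or Week 14 and who later leave, contrary to Protocol 8.4.1 and 8.7 and to SAP 2.3.2. On the other reading, the result is an omission that the endpoint definition fills.

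The number affected cannot be known from the documents. The firm figure is 2.5 points on an arm's rate per reclassified participant, which rests only on 40 per arm. A reader might infer a definite loss of power. That is not supported: the power figures rest on assumed response rates, an assumed constant hazard and assumed leaving shares, and apply only under reading A. Nor do the documents show that any participant has actually been misclassified.

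**What to change.** In SAP 5.3.1 and Appendix 1:

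- Restore the protocol's condition, so that a participant is a non-responder only if resolution of all target ulcers was not confirmed before that participant's own dropout.
- State that for a closure first seen at Week 12 the confirming assessment may be the Week 14 visit.
- State that leaving the study after confirmed resolution does not change responder status.

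If the Week 12 deadline was intended, SAP 2.1 should declare and justify it instead, and the text should say what it attaches to.

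The cost is SAP wording, plus a check that the responder derivation follows it. With the protocol wording, all seven histories above receive a single classification, and the planned sample size and power do not change.
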